1.3 Tacrolimus

Tacrolimus (FK506) is a macrolide antibiotic with immunosuppressive and anti-angiogenic properties.

1.3.1 Mechanism of action

FK506 (tacrolimus), via a dual mechanism of action, is a calcineurin inhibitor that also binds FK-binding protein-12 (FKBP12), a repressor of BMP signaling. FK506 released FKBP12 from the type I receptors activin receptor-like kinase 1 (ALK1), ALK2, and ALK3, and activated both downstream SMAD1/5 and MAPK signaling and ID1 gene regulation in a manner superior to the calcineurin inhibitor cyclosporine and the FKBP12 ligand rapamycin.³⁵

Via its binding to a specific cytoplasmic immunophilin (FKBP12), tacrolimus inhibits calcium-dependent signal transduction pathways in cells. In particular, tacrolimus inhibits the formation of cytotoxic lymphocytes, which are mainly responsible for graft rejection.

The mechanism of action of tacrolimus in atopic dermatitis is not fully understood. *In vitro*, in Langerhans cells isolated from normal human skin, tacrolimus reduced the stimulatory activity towards T cells. Tacrolimus has also been shown to inhibit the release of inflammatory mediators from skin mast cells, basophils and eosinophils. In animals, tacrolimus ointment suppressed inflammatory reactions in experimental and spontaneous dermatitis models that resemble human atopic dermatitis. Tacrolimus ointment did not reduce skin thickness and did not cause skin atrophy in animals.

In patients with atopic dermatitis, improved skin lesions during treatment with tacrolimus ointment was associated with reduced Fc receptor expression on Langerhans cells, as well as reducing their hyperstimulatory activity toward T cells. Tacrolimus ointment does not affect collagen synthesis in humans.³⁶

1.3.2 Current indications

At present, when administered either intravenously or orally, tacrolimus is used to prevent rejection following organ transplant. Tacrolimus (FK-506) is a strong immunosuppressant neutral macrolide isolated from *streptomyces tsukubaensis*. It has been used to prevent allograft rejections in the liver, kidney, lungs, and heart.^{37,38}

Tacrolimus ointment has been developed in dermatology and provides physicians with an alternative to conventional topical corticosteroid therapy for atopic dermatitis³⁹. Monotherapy is rapidly effective, resulting in clinical improvements within three days of starting therapy, and produces a progressive increase in efficacy that is sustained throughout long-term treatment. Tacrolimus treats the signs and symptoms of atopic dermatitis, reduces the incidence of flares, and offers the potential for long-term disease control.

1.3.3 Safety: Ointment safety

1.3.3.1 Skin

No major safety concerns have been reported to date. Tacrolimus ointment is generally well-tolerated, the primary adverse events being mild to moderate and transient application-site reactions: skin burning, pruritus and erythema.³⁶⁻⁴⁰

Approximately 50% of patients experienced some type of skin irritation adverse reaction at the site of application. Burning sensation, pruritus, and erythema were very common, usually mild to moderate in severity and tended to resolve within one week of starting treatment. Increased skin sensitivity and skin tingling were also common skin irritation adverse reactions. Alcohol intolerance (facial flushing) was common. Patients may be at an increased risk of folliculitis, acne, and herpes simplex.³⁶

Three published observational studies have assessed the carcinogenic risk on large cohorts of patients:

- The retrospective Arana study (2010)⁴¹ compared the incidence of cancer in the general population and in patients with atopic dermatitis. It focused on a cohort of 4,456,008 patients with no history of cancer from "The Health Improvement Network" database, representative of the population of the United Kingdom. This study showed a higher incidence of skin cancer in atopic patients, but it did not make it possible to establish a link between skin cancer and treatment for atopic dermatitis.
- Hui (2009)⁴² studied safety in a retrospective cohort. Of the 11,961 cancer cases reported between 2001 and 2005, no difference was observed for all forms of cancer combined between patients exposed or not exposed to calcineurin inhibitors after adjustment according to age and sex.
- Schneeweiss⁴³ studied a cohort of 1,252,300 patients, to assess the risk of lymphoma during treatment with tacrolimus, pimecrolimus or corticosteroids. Compared to the general population, these three treatments were associated with an increased risk of occurrence of lymphoma. Compared to patients with untreated

atopic dermatitis, however, the three treatments were not associated with an increased risk of lymphoma.

An open-label multicenter trial in children has been performed to evaluate safety. Skin infections occurred in 26% of patients. A burning sensation with product application, reported by 38% of patients, was transient and of mild-to-moderate severity in most cases. They concluded that Tacrolimus 0.1% ointment was safe, well-tolerated, and efficacious in the treatment of atopic dermatitis in children over the age of six months and adults ⁴⁴.

Long-term safety was studied in a systematic review of published trials with long term treatments (at least 12 weeks)⁴⁵. Data from 9 trials using tacrolimus were collected i.e. 1370 patients, treatment duration varied from 12 weeks to 5 years. This review supports the long-term safety with no evidence of cutaneous atrophy or cumulative systemic exposure and no reports of lymphoma⁴⁵.

1.3.3.2 Mucosae

To evaluate the tolerability of tacrolimus on mucosae (tacrolimus 0.3 mg g(-1) ointment), in the treatment of chronic plaque psoriasis affecting facial and genitofemoral regions, a double-blind, parallel, 6-week study was carried out on 50 patients who were randomized in a 1 : 1 ratio to apply calcitriol or tacrolimus twice daily. The authors concluded that both calcitriol 3 microg g(-1) and tacrolimus 0.3 mg g(-1) are safe and well-tolerated therapeutic agents in the treatment of psoriasis in sensitive areas. Tacrolimus demonstrated a more effective clinical outcome compared with calcitriol. ⁴⁶

Tolerability has been evaluated in the treatment of oral lichen planus (OLP). Corrocher reported in the group treated with tacrolimus, nine of 16 patients (56.3%) who had an initial worsening of burning sensation during the first 2 days of treatment. However, it resolved rapidly within 4–5 days as OLP improved⁴⁷, Vohra et al reported a transient burning sensation by seven patients (six in the tacrolimus and one in the pimecrolimus group), and two patients complained of dysgeusia following tacrolimus application. No serious adverse effects necessitating stopping treatment were recorded in the two groups.⁴⁸. More recently, Arduino et al published a randomized study treated with tacrolimus or piperolimus. Among them, in the tacrolimus group, two patients reported mucosal burning sensation during the first days of the therapy and one reported a transient sialorrhoea. In the pimecrolimus group, two patients reported xerostomia, two experienced episodes of gastroesophageal reflux and one the recurrence of two lesions of herpes labialis. None of these adverse effects was severe enough to require discontinuation of therapy. There were no statistically significant differences between the two groups in the incidence of adverse effects⁴⁹ and Sonthalia et al compared the efficacy of clobetasol propionate (0.05%) ointment or tacrolimus (0.1%) ointment for eight weeks in 40 patients. None of the patients in either group showed any abnormality in hematological or biochemical parameters at eight weeks of treatment and no severe adverse events were reported. The majority of patients in both treatment groups reported good local tolerance to the topical drugs. Three patients in the tacrolimus group (15%) and three in the clobetasol group (15%) complained of a transient burning sensation following the application of the ointment, which lasted for a few seconds to a few minutes and did not necessitate the discontinuation of therapy. No patient

developed any clinically detectable atrophy, pigmentation, telangiectasia, or any type of allergic reaction.⁵⁰

1.3.3.3 Ophthalmic

Tacrolimus ointment can be used by opthalmic route for ocular diseases treatments, several studies were published:

Barot RK⁵¹ studied effect 0.1% tacrolimus ointment in allergic ocular diseases on 36 patients.

Fukushima A⁵² investigated efficacy of topical 0.1% tacrolimus eye drops for allergic ocular diseases on a cohort of 1436 patients.

Chatterjee S⁵³ in an open-label study enrolled 30 patients with vernal keratoconjunctivitis, they were treated with 0.03% tacrolimus eye ointment for at least 4 weeks.

Shoughy S⁵⁴ studied efficacy and safety of topical tacrolimus 0.01% solution on 62 patients with vernal keratoconjunctivitis.

In all cases the treatment was well tolerated, no serious adverse event was observed, the most common adverse reaction was a transient burning sensation, rare corneal infections were described, one bacterial corneal ulcer and one trachoma.

1.3.4 Pharmacokinetic and systemic absorption

Data from healthy human subjects indicate that there is little or no systemic exposure to tacrolimus following repeated topical application of tacrolimus ointment. As systemic exposure is low with tacrolimus ointment, the high binding of tacrolimus to plasma proteins is not considered to be clinically relevant. The metabolism of tacrolimus by human skin was not detectable. Systemically-available tacrolimus is extensively metabolized in the liver via CYP3A4. Following repeated topical application of the ointment, the average half-life of tacrolimus was estimated to be 75 hours for adults and 65 hours for children.³⁶

Several studies in infants^{55,56} on the pharmacokinetics of tacrolimus after first and repeated application showed minimal systemic exposure. 92% of blood samples contained tacrolimus concentrations of less than 1 ng per mL and 17% of samples were less than 0.025 ng per mL (lower limit of quantification). These values are minimal compared with an oral dose after a liver transplant. Systemic exposure to tacrolimus increased in proportion to the size of the body surface treated, and decreased with time as the skin lesions healed. There was no evidence of systemic accumulation.

Further to an administration on mucosae, pharmacokinetic was evaluated in two clinical trials and no systemic absorption was detected^{47,49}.

1.4 Tacrolimus and HHT

In vitro, Albinana et al.⁵⁷ reported the efficacy of tacrolimus (FK506) in increasing ENG and ALK1 protein levels at the surface of endothelial cells; it also increases the expression of ENG and ALK1 mRNA and ENG and ALK1 promoter activity in cultured endothelial cells, and enhances the TGF- β 1/ALK1 signaling pathway and endothelial cell functions such as tubulogenesis and migration.

Furthermore, we know that after HHT patients have had a liver transplant for hepatic AVMs and high-output cardiac failure, their epistaxes improve dramatically⁵⁸ and mucosal bleeding stops. Their hemoglobin levels normalize and cutaneous and gastrointestinal telangiectases disappear.

This suggests that the immunosuppressive therapy might have had anti-angiogenic effects on the telangiectases⁵⁹, and that the mechanism of action of FK506 involves a partial correction of endoglin and ALK1 haploinsufficiency. It may therefore be an interesting drug for use in HHT patients.

It has recently been reported (HHT Meeting, Florida 2015) by Feige et al., in the HHTreat project that aims to identify new drugs that could be of interest in the treatment of HHT patients, that tacrolimus would be a good candidate.

The antiangiogenic effect of tacrolimus has been demonstrated in other vascular diseases. *In vitro*, in pulmonary artery endothelial cells (ECs) from patients with idiopathic pulmonary arterial hypertension (PAH), low-dose FK506 reversed dysfunctional BMPR2 signaling. In mice with conditional Bmpr2 deletion in ECs, low-dose FK506 prevented exaggerated chronic hypoxic PAH associated with the induction of the EC targets of BMP signaling, such as apelin. Low-dose FK506 also reversed severe PAH in rats with medial hypertrophy following monocrotaline and in rats with neointima formation following VEGF receptor blockade and chronic hypoxia. These data indicate that low-dose FK506 could be useful in the treatment of PAH.³⁵. More recently, sirolimus (rapamycin), which also binds FK-binding protein-12 (FKBP12), is safe and efficient in the treatment of Blue rubber bleb nevus syndrome, a rare multifocal venous malformation syndrome involving predominantly the skin and gastrointestinal tract⁶⁰ or other vascular malformations⁶¹.

A recent study on corneal neovascularization in rabbits compares the antiangiogenic effects of tacrolimus and bevacizumab. They conclude that topical or subconjunctival administration of tacrolimus reduces experimental CNV, shown by the decreased levels of VEGF, macrophages, TNF- α , IL-1 β and MCP-1.⁶²

2 Justification for the study

2.1 Rationale for the study

To date, no surgical treatment has made it possible to significantly decrease nosebleeds – the most common complication of the disease, responsible for significant morbidity – in the medium to long term in patients with HHT. Moreover, surgical treatments are aggressive for the nasal mucosa and risk perforating the nasal septum.

Intra-venous anti-VEGF treatment is efficient on epistaxis¹, but its use is limited to severe forms of the disease, and local administration (nasal spray) recently evaluated in a phase 2 study is not efficient (NCT02106520)⁶³.

Improved epistaxes have been observed in HHT patients after a liver transplant. It was hypothesized that the immunosuppressive treatment (FK506) used to prevent rejection may have an anti-angiogenic effect.

A topical nasal administration of tacrolimus could be an easy local ENT treatment that is non-aggressive and results in little trauma for the patient in relation to other first line treatment possibilities. Moreover, a galenic ointment with tacrolimus is available on the market.

2.2 Safety and rationale for the pharmaceutical form, means of administration and doses used

The pharmaceutical form retained for this phase II study is an ointment: Protopic® 0.1%, packaged in tubes of 30 g. This marketed product (market authorization EU/1/02/201/003) is prescribed to treat severe atopic dermatitis.

In the study, this ointment can be used as is in the nose.

Nasal administration of tacrolimus ointment and its safety is unknown. Nevertheless data published on mucosae and ophthalmic route are encouraging, tacrolimus ointment is generally well tolerated including long-term treatments. Burning sensation is the most common reaction but it is transient and usually without treatment interruption.

As safety and pharmacokinetics have been extensively studied in dermatitis, we decided to use the same posology, i.e. twice daily.

For a nasal administration, the quantity applied will be about 0.1 g in each nostril; it represents 0.4 g of ointment per day i.e. 0.4 mg of tacrolimus.

In order to show efficiency, the treatment period has to be long enough to heal lesions responsible for epistaxis and to decrease vascularization. The longer period treatment recommended on SmPC has been chosen, that is to say 6 weeks.

The risk of systemic effect is limited because of the low doses prescribed. The administered dose is 0.4 g of ointment per day, that is to say 0.4 mg of tacrolimus per day.

Transplant patients treated with tacrolimus by oral route receive a dose from 0.1 to 0.2 mg / kg / day (i.e. 5 to 10 mg per day for a 50 kg person). The dose on IV route is 0.01 to 0.05 mg/kg/day (i.e. 0.5 to 3 mg per day for a 50 kg person).

Although systemic absorption was not observed after administration on mucosae^{47,49}, if a systemic absorption occurs, no adverse reactions are expected given the low doses and the good tolerance of tacrolimus per os.

It should be noted that the risk of overdosage is very low in this study, since the application of ointment in the nose can cause discomfort for the patient, it is unlikely that the patient will increase the doses to be administered.

Tacrolimus systemic absorption will be monitored in this study. FK506 dosages in blood are scheduled at Day 8, 22 and 43. Analysis will be centralized in "Hospices Civils de Lyon".

After transplantation, the optimal trough blood concentrations are generally between 5.0 and 15.0 ng/mL⁶⁴ and should be maintained below 20 ng/mL.

In the present study, no systemic absorption and effect are expected. However in case of positive dosage, from 5 ng/mL and above, the laboratory will immediately inform the investigator who will ask the patient to stop treatment.

In case of dosage higher than 20 ng/mL, the laboratory will immediately inform the investigator who will ask the patient to stop treatment and the patient will be hospitalized.

The placebo formulation is strictly identical to Protopic: it contains all the ingredients except tacrolimus. The packaging is similar. The posology is also twice daily.

2.3 Rationale for the methodology

The methodology retained for this efficacy (phase II) study is a randomized trial, which is the design presenting the highest level of evidence.

We started to assess parameters by comparing data collected at 3 visits:

- Visit 1: inclusion, data collected for 6 weeks before treatment and during the visit
- Visit 2: end of treatment, data collected during the 6 weeks preceding the visit (i.e. 6 weeks of treatment) and during the visit
- Visit 3: end of study, data collected during the 6 weeks preceding the visit (i.e. 6 weeks following the end of treatment) and during the visit.
- In addition, data are collected on pharmacokinetic at Day 8 and Day 22 (blood sample) and on safety at Day 15 and Day 31 (phone call).

[figure not shown]

Figure 4 General diagram of the study

For safety reasons, as no tolerance data are available with a nasal administration, we decided to include patients sequentially. We designed an inclusion scheme in 3 or 4 steps. An independent safety committee will give its recommendations on the continuation of the study.

The theoretical inclusion scheme is described as follows. It was established pragmatically based on our sample size.

We consider that a cessation of treatment for at least 8 consecutive days, for safety concern, that is to say adverse reaction due to the ointment, is a major issue.

- **STEP 1- 8 patients will be included in Lyon.**

On day 31 (phone call): information regarding adverse events (AE), severe adverse events (SAE) and observance of the treatment for the first 30 days of treatment are collected for these 8 patients.

Based on these data, a DSMB meeting (#1) will be consulted and will give its recommendations on the continuation of the study according to the following theoretical scheme:

Number of patient who stop treatment for 8 consecutive days		ARM PLACEBO				
		0	1	2	3	4
ARM ACTIV	0	0	1	2	3	4
	1	1	2	3	4	5
	2	2	3	4	5	6
	3	3	4	5	6	7
	4	4	5	6	7	8

The numbers inside the table = total number of events in both arms

	No imbalance between arms
	Imbalance between arms active>placebo
	Imbalance between arms placebo>active
	+ 16 patients
	+ 8 patients
	Stop

If there is no imbalance between arms (difference ≤ 1), the total number of patient who stop treatment at least 8 consecutive days will be consider (semi-blind data transmitted to DSMB):

- < 4 patients in both arms \rightarrow inclusion of 16 new patients (Step 2A)
- ≥ 4 patients in both arms \rightarrow inclusion of 8 new patients (Step 2B)

Note: if a large number of patients stopped the treatment for at least 8 consecutive days, the hypothesis will be that the ointment form is not well accepted. Then we consider it is worthwhile to check this point by including 8 additionnal patients.

If there is an imbalance between arms (difference > 1), (unblinded data will be transmitted to DSMB):

- The number of “stops” is higher in the placebo arm
 - If “0” or “1” patients in active arm stop treatment \rightarrow inclusion of 16 new patients (**Step 2A**)
 - If “2” patients in active arm stop treatment \rightarrow inclusion of 8 new patients (**Step 2B**)
- The number of “stops” is higher in the active arm
 - If difference between arms is 2 \rightarrow inclusion of 8 new patients (**Step 2B**)
 - If difference between arms is over 2 \rightarrow inclusions may be discontinued (**Step 2C**).

The first 8 patients will be included in the Lyon center. Further inclusions will take place in all centers.

For the following steps, we consider the total number of patients who have a cessation of treatment for at least 8 consecutive days for safety concerns. Indeed, if 50% or more of patients are “in failure”, the continuation of the study may be called into question and the analysis on the main judgement criteria will then not be relevant.

- **STEP2 – Following inclusions, all centers**

STEP 2A- In case of inclusion of 16 new patients.

For these 16 patients, on day 31 (phone call): information regarding adverse events (AE), severe adverse events (SAE) and observance of the treatment for the first 30 days of treatment are collected. Additionally, safety assessment is carried out on the data collected at the visit after the end of treatment for the first 8 patients.

Based on these data, a DSMB meeting (#2) will be consulted and will give its recommendations on the continuation of the study according to the following theoretical equations:

- If less than 12 of the 24 patients stop treatment for 8 consecutive days due to safety concerns, 24 new patients will be included (**Step 3A**). Total number of patients included: $8 + 16 + 24 = 48$.
- If 12 or more patients stop treatment for at least 8 consecutive days due to safety concerns, depending on the group imbalance, the DSMB may request the lifting of the blind and inclusions may be discontinued (**Step 3B**). Total number of patients included: $8 + 16 = 24$.

STEP 2B- In case of inclusion of 8 new patients.

For these 8 patients, on day 31 (phone call): information regarding adverse events (AE), severe adverse events (SAE) and observance of the treatment for the first 30 days of treatment are collected. Additionally, safety assessment is carried out on data collected at the visit after the end of treatment for the first 8 patients.

Based on these data, a DSMB meeting (#2) will be consulted and will give its recommendations on the continuation of the study according to the following theoretical equations:

- If less than 8 patients stop treatment for 8 consecutive days due to safety concerns, 16 new patients will be included (**Step 3C**).
- If 8 or more patients stop treatment for at least 8 consecutive days due to safety concerns, depending on the group imbalance, the DSMB may request the lifting of the blind and inclusions may be discontinued (**Step 3D**). Total number of patients included: $8 + 8 = 16$.

- **STEP3 – Following inclusions, all centers**

STEP 3A- Inclusion of 24 new patients, total number of patients included = 48

STEP 3C- In case of inclusion of 16 new patients.

For these 16 patients, on day 31 (phone call): information regarding adverse events (AE), severe adverse events (SAE) and observance of the treatment for the first 30 days of treatment are collected. Additionally, safety assessment is carried out on data collected at the visit after the end of treatment for the first 16 patients.

Based on these data, a DSMB meeting (#3) will be consulted and will give its recommendations on the continuation of the study according to the following theoretical equations:

- If less than 16 patients stop treatment for 8 consecutive days due to safety concerns, 16 new patients will be included (**Step 4A**).
- If 16 or more patients stop treatment for at least 8 consecutive days due to safety concerns, depending on the group imbalance, the DSMB may request the lifting of the blind and inclusions may be discontinued (**Step 4B**). Total number of patients included: $8 + 8 + 16 = 32$.
- **STEP4 – Following inclusions, all centers**

STEP 4A- Inclusion of 16 new patients, total number of patients included = 48

[figure not shown]

Figure 5: Inclusions flow chart

3 Objectives

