6.1 General organization and study sites

Patients will be recruited and informed during a standard consultation with the ENT doctor or doctor responsible in the reference center or skill center for HHT. Patients will be informed of the study and the need to complete nosebleed grids for ENT monitoring for the 6 weeks prior to the start of the treatment (Appendix 1: Nosebleed monitoring grid, a grid completed daily by patients).

The inclusion of the patients will take place when they come for a consultation for prescription of the treatment.

The treatment will be self-administered by the patient, twice daily, for 6 weeks.

Two follow-up visits are organized, at the end of the 6 weeks of treatment, and 6 weeks after the end of the treatment, with medical consultations in the department responsible for coordinating HHT (Reference or skill center) and in the ENT department of each center.

FK-506 dosage in blood are scheduled on Day 8, 22 and 43.

A phone call is scheduled on day 15 and 31 (i.e. 14 and 30 days after the beginning of the treatment) in order to collect information regarding tolerance and observance.

[figure not shown]

Figure 8: Diagram of the running of the study

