- Drug dispensation: The prescription for the drug will be made, and the product will be delivered by the pharmacist at the hospital. Patients are carefully instructed how to apply the medication through an in vivo demonstration and a written description is provided with the product in which the modalities of application are reported.
- A clinical trial participation card will be given to the patient. It will include phone numbers if needed and in case of emergency. Recommendations are given in case of the onset adverse events.
- A specific prescription will be given to the patient for the dosage of FK506 in blood, one week and three weeks after the beginning of the treatment (i.e. on Day 8 and Day 22). Blood sample will be taken in a laboratory selected by the patient; the latter will send the tube in the biological laboratory for a centralized analysis.

If the criteria are not validated, the patient may be asked to return at a later date if the inclusion criteria can be normalized.

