6.7 Synopsis of the study per patient

	Inclusion V1 J0	Blood sample D8 (to 10)	Phone Call D15 (to 18)	Blood sample D22 (to 24)	Phone Call D31 (to 37)	V2 D43 (to 50)	V3 D85 (to 100)
Inclusion / exclusion criteria	x						
Epistaxis grids surrender	x		x		x	x	
Epistaxis grids collection	x					x	x
Consent Form signature	x						
Pregnancy Test	x						
Clinical examination (HR, BP)	x					x	x
ENT examination	x					x	x
Hémoglobinemia, serum ferritin	x					x	x
FK 506 dosage		x		x		x	
Treatment : protopic/placebo dispensation	x						
Product return						x	
Blood Cell transfusions collection	x					x	x
ESS questionnaire	x					x	x
SF36 Quality of life questionnaire	x					x	x
Concomitant treatment collection	x		x		x	x	x
Adverse events collection	x		x		x	x	x

Legend: D = day V = visit

Table 1: Synopsis of the study per patient

7 Intercurrent events

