7.4.4 Tacrolimus systemic absorption

Tacrolimus systemic absorption will be monitored in this study. FK506 dosages in blood are scheduled at Day 8, 22 and 43. Analysis will be centralized in "Hospices Civils de Lyon".

After transplantation, the optimal trough blood concentrations are generally between 5.0 and 15.0 ng/mL⁶⁴ and should be maintained below 20 ng/mL.

In the present study, no systemic absorption and effect are expected. However in case of positive dosage, from 5 ng/mL and above, the laboratory will immediately inform the investigator who will ask the patient to stop treatment.

In case of dosage higher than 20 ng/mL, the laboratory will immediately inform the investigator who will ask the patient to stop treatment and the patient will be hospitalized.

Any sign of infection due to immunosuppressive action should be reported immediately to the sponsor as SAE.

8 Data management

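### At the day-31 reading, the count that drives the inclusion steps cannot include a safety stop that begins on days 24-30

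*Combined protocol and SAP*

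**What the plan says.** Section 2.3 includes patients in steps because nasal tolerance is unknown. The event it counts is "a cessation of treatment for at least 8 consecutive days, for safety concern, that is to say adverse reaction due to the ointment". For Step 1, adverse events, serious adverse events and "observance of the treatment for the first 30 days of treatment are collected for these 8 patients" at the day-31 call. Steps 2A, 2B and 3C read their new cohorts in the same way. At the second meeting the DSMB also receives end-of-treatment safety data on the first 8 patients, and at the third on the first 16.

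Section 6.1 fixes the day numbering: "A phone call is scheduled on day 15 and 31 (i.e. 14 and 30 days after the beginning of the treatment". Sections 6.4 and 6.7 tolerate the later call up to day 37. Section 6.4 has the caller record the date, duration and reason of any interruption.

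On absorption, sections 2.2 and 7.4.4 state that "FK506 dosages in blood are scheduled at Day 8, 22 and 43". Section 6.7 allows the day-22 sample up to day 24. Section 6.2 says of the day-8 and day-22 samples: "Blood sample will be taken in a laboratory selected by the patient"; the tube is then sent on for central assay. Under 7.4.4, "from 5 ng/mL and above, the laboratory will immediately inform the investigator who will ask the patient to stop treatment". Section 7.1.2 makes a level above 5 ng/mL a serious adverse event.

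**The concern.** The event needs 8 days to complete, and the window closes 30 days after the start. A patient who stops for good on day 24, 27 or 30 because of a reaction has been off ointment for at most 7 days when the window closes, and enters the step table as no event. The caller will already have recorded that stop.

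The text leaves three related points open:
- whether a stop still running at the call counts;
- whether a call made on days 32-37 extends the 30-day window, so that the same stop could count or not depending on the call date;
- whether a stop made only because of a blood level is an adverse reaction due to the ointment, and so whether it counts at all.

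The first meeting advises on moving from 8 patients in one centre to all centres. The numbers are so small that a single event can decide the recommendation. The count also settles whether the DSMB receives semi-blind or unblinded data.

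**Working it through.** The plan gives no figure for the latest countable stop, so it is derived here.

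**Inputs.** Event length 8 days and window days 1-30 (2.3); day 31 is 30 days after the start, so treatment starts on day 1 (6.1); treatment lasts 42 days; call on day 31, up to day 37 (6.4, 6.7); samples on day 8 (to 10) and day 22 (to 24) (6.7).

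**Cut-off.** If observance is read through day E, the latest first day off that completes 8 days is E - 7.

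- E = 30: day 23. A stop from day 23 gives 8 days and counts; from day 24 it gives 7 and does not.
- E = 36 (a day-37 call read through the previous day): day 29.
- E = 42 (end of treatment): day 35.

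**Share of treatment affected.** Days 24-30 are 7 days; 7/42 = 17%. Days 31-42 (12 days) come after the look, and any day-31 review misses them however the event is defined.

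**Patients read only to day 30 at each decision.** First meeting: 8 of 8. Second meeting: 16 of 24 (path 2A) or 8 of 16 (path 2B). Third meeting: 16 of 32. In path 2A the 16 Step 2 patients have no later scheduled decision. The same is true of the 16 Step 3C patients.

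**Stops prompted by the week-3 sample.** First day off = sample day + L, where L is the lag in days. L is not in the documents, so it is varied. An even spread of samples over days 22-24 is also an assumption.

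| L (days) | Missed, samples spread over days 22-24 | Missed, all samples on day 22 |
|---|---|---|
| 0 | 1/3 | none |
| 1 | 2/3 | none |
| 2 to 5 | all | all |

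These are for E = 30. With E = 36, none is missed for L = 0 to 5.

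**Day-8 sample.** The latest permitted draw is day 10, and 23 - 10 = 13. Such a stop is counted if it begins within 13 days of sampling and lasts 8 days.

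**Effect at Step 1** (rules of 2.3, table laid out for 4 per arm), when one active-arm stop is not counted:

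| True stops, active v placebo | Scheme on true count | Count seen | Scheme on count seen |
|---|---|---|---|
| 3 v 0 | difference 3: inclusions may cease | 2 v 0 | difference 2: 8 more |
| 2 v 0 | difference 2: 8 more, unblinded data | 1 v 0 | difference 1, total 1: 16 more, semi-blind data |
| 3 v 1 | difference 2: 8 more | 2 v 1 | difference 1, total 3: 16 more |
| 4 v 2 | difference 2: 8 more | 3 v 2 | difference 1, total 5: 8 more (no change) |

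At later meetings the thresholds are totals (12 of 24, 8 of 16, 16 of 32), so one missed stop matters only at the margin.

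**The case against.** The strongest case on the other side has five parts.

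1. **The DSMB is not blind to these stops.** It receives adverse events, serious adverse events and observance as well as the count, and a level above 5 ng/mL must be reported as serious. The scheme is described as theoretical and the committee only recommends. This stands. A reader might infer that such stops escape the DSMB altogether; the documents do not support that. They escape the number on which the written rule acts.

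2. **Later data repair part of the gap.** End-of-treatment data on earlier cohorts reach the next meeting, where a stop beginning up to day 35 can be seen. This stands for those cohorts, but comes one decision late and never reaches the Step 2 patients of path 2A.

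3. **Absorption is checked earlier.** A reader might take day 22 as the only mid-course check, but day 8 is another. Suppose absorption is constant and the 75-hour half-life given for skin in 1.3.4 applies in the nose (both assumptions). The day-8 level is then 1 - 2^(-168/75) = 79% of steady state and the day-22 level 1 - 2^(-504/75) = 99%. A patient above about 5 x 0.99/0.79 = 6.3 ng/mL on day 22 would already have reached 5 on day 8. Stops first arising at week 3 may therefore be uncommon. The protocol also expects no absorption.

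4. **Reactions come early.** Section 1.3.3.1 expects irritation mostly to settle within a week, so stops spread evenly over treatment are not the likely pattern. A reader might quote 19 of 42 days (45%) as uncounted. That adds the 12 days after a deliberate early look to the 7 that the 8-day rule costs.

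5. **The 8-day rule filters out short pauses.** Section 6.2.2 allows reintroduction after a reaction. Counting every pause in progress at the call would add false events, each able to shift Step 1 as much as a missed one. This stands and shapes the fix.

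None of this changes the arithmetic for days 24-30.

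**Conclusion.** The point holds in a limited form. On the 30-day reading, a safety stop that begins on days 24-30 cannot enter the step count at its cohort's decision, even if it is definitive. That is 7 of 42 treatment days (17%). The share of stops lost is not known: it equals 17% only if stops are spread evenly over treatment, and would be smaller if they cluster early.

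For stops prompted by the week-3 sample, all are missed if the first day off comes 2 or more days after sampling. At a lag of 0 or 1 day, none to two thirds are missed, depending on sample day. A reader might infer that nearly all such stops are lost. A tube sent on to a central laboratory makes a lag of 2 days plausible, but no turnaround is stated, and a late call read through day 36 would capture every stop with a lag of 0-5 days. Stops from the day-8 sample are normally captured.

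The consequence is greatest at Step 1, where one uncounted active-arm stop can move the scheme from possible cessation of inclusions to 8 more patients, or from 8 more to 16 more. The rule should be changed before the first meeting.

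**What to change.** In 2.3 and the DSMB report template:

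- Do not close the count at day 30. Carry forward any safety stop still running at the day-31 call, and update its duration for all patients included so far just before each meeting.
- Count the stop if it has reached 8 consecutive days or if treatment has been definitively stopped. List running stops shorter than 8 days separately by arm, under the existing semi-blind and unblinded rules, without counting them automatically.
- State one reading date, given the call tolerance to day 37. A stop that begins on day 30 completes its eighth day on day 37 (30 + 7), so an update after that day settles every stop begun by day 30.
- Reconcile the event definition in 2.3 with 7.1.2 and 7.4.4, so that it is clear whether a stop for a tacrolimus level is counted.

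The cost is a wording change and one short status check before each meeting. The call already collects date, duration and reason. A few more events may be counted. No patient's treatment changes.
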